10.3.1.2 Safety Analyses

All AEs reported during the study will be listed, documenting onset, whether therapy was required, any change in study treatment dosing, severity, possible relationship to study treatment, and outcome. Verbatim terms on the eCRFs will be linked to preferred terms (PTs) and system organ class (SOC) using the Medical Dictionary for Regulatory Activities (MedDRA) mapping system.

TEAEs are defined as AEs that first occur or worsen in severity after the first administration of study treatment and prior to 30 days after the last administration of study treatment. All reported TEAEs and incidence rates will be summarized by the number of subjects reporting AEs, SOC, PT, severity, and relationship to study treatment by treatment group.

TEAEs by maximum severity, TEAEs by relationship to study treatment, SAEs, TEAEs leading to death, and TEAEs leading to discontinuation of study treatment will be tabulated for each treatment group. Commonly occurring TEAEs, i.e., those that occur in 5% or more of the subjects in either treatment group, will be summarized using descriptive statistics. TEAEs and relevant patient years of exposure will be presented, as appropriate.

All laboratory test results, vital signs measurements, and weight will be summarized for each treatment group using descriptive statistics for raw numbers and change from Baseline. The incidence of treatment-emergent clinically significant laboratory and vital signs values will also be summarized using descriptive statistics.

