- The Investigator will also consult the Investigator's Brochure and/or Product Information, for marketed products, in his/her assessment.
- For each AE/SAE, the Investigator must document in the medical notes that he/she has reviewed the AE/SAE and has provided an assessment of causality.
- There may be situations in which an SAE has occurred, and the Investigator has minimal information to include in the initial report to Advanced Clinical - Global Safety Services. However, it is very important that the Investigator always make an assessment of causality for every event before the initial transmission of the SAE data to Advanced Clinical - Global Safety Services.
- The Investigator may change his/her opinion of causality in light of follow-up information and send an SAE follow-up report with the updated causality assessment.
- The causality assessment is one of the criteria used when determining regulatory reporting requirements.

Follow-Up of AEs and SAEs

- The Investigator is obligated to perform or arrange for the conduct of supplemental measurements and/or evaluations as medically indicated or as requested by Advanced Clinical - Global Safety Services to elucidate the nature and/or causality of the AE or SAE as fully as possible. This may include additional laboratory tests or investigations, histopathological examinations, or consultation with other health care professionals.
- If a subject dies during participation in the study or during a recognized follow-up period, the Investigator will provide Advanced Clinical - Global Safety Services with a copy of any postmortem findings including histopathology.
- New or updated information will be recorded in the originally completed eCRF.
- The Investigator will submit any updated SAE data to the Sponsor/Advanced Clinical - Global Safety Services within 24 hours of receipt of the information.

Reporting of SAEs

SAE Reporting via Paper CRF

- E-mail transmission of the SAE paper CRF is the preferred method to transmit this information to Advanced Clinical - Global Safety Services with Facsimile transmission as back-up method.
- In rare circumstances and in the absence of e-mail/facsimile equipment, notification by telephone is acceptable with a copy of the SAE data collection tool sent by overnight mail or courier service.
- Initial notification via telephone does not replace the need for the Investigator to complete and sign the SAE eCRF pages within the designated reporting time frames.

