1.3.1 Overview of Study Design

The study consists of three periods:

- **Period 1 – Induction (3 weeks):**

At the beginning of the 3-week induction period, eligible subjects will be randomized (2:1 ratio) to either TMB-001 0.05% once-a-day (QD) or Vehicle QD treatment, with use of mandatory standardized bland emollient (Cetaphil™) provided by the Sponsor.

- **Period 2 – Treatment (9 weeks):**

The dosing frequency in the 9-week treatment period will be increased in each treatment group to TMB-001 0.05% or Vehicle twice a day (BID). Mandatory bland emollient will be discontinued.

- **Period 3 – Maintenance (12 weeks):**

At Week 12, eligible subjects in the TMB-001 treatment group will be randomized (1:1 ratio) to open-label treatment with TMB-001 0.05% BID or QD. To be eligible, subjects must have achieved a \geq 1-point reduction in IGA score from Baseline.

Subjects with $<$ 1-point reduction in IGA score from Baseline will be discontinued from the study.

Vehicle-treated subjects who achieved $<$ 1-point reduction in IGA score from Baseline are eligible to cross over to the TMB-001 0.05% BID treatment group. Subjects with a \geq 1-point reduction in IGA score from Baseline will be discontinued from the study.

Subjects at the end of the study or subjects discontinued from the study at any time will be followed-up for an additional 2 weeks for the monitoring of adverse events.

Optional Maximal Use Arm

Adult and pediatric subjects, at a subset of preselected centers, will be enrolled in an open-label Optional Maximal Use arm to evaluate the systemic exposure and safety of topical TMB-001 0.05% ointment for the treatment of CI under maximal use conditions. Initially, adult CI subjects (\geq 17 years; n=16) and pediatric subjects (12-16 years; n=7-9) will be dosed for 14 days with TMB-001 0.05% BID. Following an interim PK analysis and based on the exposure data for subjects aged \geq 12 years, pediatric subjects aged 6 to 11 years (n=7-9) will begin dosing with TMB-001 0.05% BID for 14 days. Following the 14-day PK assessment period, subjects will receive TMB-001 0.05% BID treatment for 10 additional weeks to provide additional safety and limited efficacy data.

The schedule of assessments for both the Phase 3 study and the optional maximal use arm can be found in the study protocol.

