3.4 Baseline Definitions

Unless otherwise noted, baseline is defined as the last non-missing measurement prior to the first administration of study drug. It is expected that all baseline measurements are taken on Visit 2, for all subjects.

For the DLQI, cDLQI, and IQoL-32, baseline is defined as the nominal 'Baseline' visit as reported in the PRO ediary, regardless of when this baseline record is reported.

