7.2 Adverse Events

All adverse events (AEs) will be coded using the MedDRA v25.0 coding system and displayed in tables and data listings using system organ class (SOC) and preferred term. Missing and partial dates will be handled as described in Section 3.9.2.

Analyses of AEs will be performed for those events that are considered treatment-emergent, where treatment-emergent is defined as any AE with onset after the first application of study drug through 30 days after the last study drug application, or any event that was present at baseline but worsened in intensity or was subsequently considered drug-related through 30 days after the last study drug application.

Adverse events will be summarized by subject incidence rates; therefore, in any tabulation, a subject contributes only once to the count for a given AE in both SOC and preferred term. The table will be sorted by descending frequency, based on the overall column of the data presentation.

Adverse events will be reported separately by event type; reporting of SOCs and preferred term will be as described above.

The number and percentage of subjects with any treatment-emergent adverse event (TEAE), with any TEAE assessed as related to study drug (possibly or probably), with any serious TEAE, any non-serious TEAE, with any serious TEAE potentially related to study drug, any non-serious TEAE potentially related to study drug, with any common (occurring in $\geq 5\%$ of subjects) TEAE, or with any TEAE leading to study drug withdrawal will be provided. Additional tabulations will be provided for TEAEs by maximum severity, and TEAEs by strongest relationship to study drug.

All analyses above will be performed using both data presentations described in Section 3.9.3, where TEAEs will contribute to each summary only if they began in the corresponding period. For example, a TEAE starting during Periods 1 or 2 will be reported using the primary safety data presentation, and a TEAE starting during Period 3 will be reported using the open-label dosing data presentation.

Additionally, the proportion of subjects experiencing a TEAE through Week 12 will be reported along with exact binomial 95% confidence intervals, using the primary safety data presentation. The proportion of subjects experiencing a TEAE through Week 24 will be reported along with exact binomial 95% confidence intervals, using the open-label dosing data presentation.

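### SAP 7.2 assigns TEAEs to period tables by start alone, so worsening in Period 3 is missing from the open-label table and can be shown under the initial arm, including Vehicle

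*SAP*

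**What the plan says.** SAP 7.2 gives two routes to a TEAE. One is onset after the first application. The other is "any event that was present at baseline but worsened in intensity or was subsequently considered drug-related through 30 days after the last study drug application". Protocol 10.3.1.2 also counts worsening: "TEAEs are defined as AEs that first occur or worsen in severity after the first administration of study treatment".

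For the period tables, SAP 7.2 then says that "TEAEs will contribute to each summary only if they began in the corresponding period". It illustrates this by start date: "a TEAE starting during Periods 1 or 2 will be reported using the primary safety data presentation", while one starting in Period 3 goes to the open-label presentation. The rule covers the analyses listed before it, which include serious TEAEs, related TEAEs, TEAEs leading to withdrawal, maximum severity and strongest relationship.

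Four other provisions decide how the rule works out:

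- SAP 3.4: unless otherwise noted, "baseline is defined as the last non-missing measurement prior to the first administration of study drug". No new reference is set at the start of Period 3.
- SAP 3.11.3: the TMB-001 and Vehicle columns of the primary safety presentation follow the initial randomization, whatever happens in Period 3.
- SAP 1.3.1: vehicle subjects with less than a 1-point IGA reduction at Week 12 "are eligible to cross over to the TMB-001 0.05% BID treatment group".
- SAP addendum 6.0: for a subject with an event, the time at risk for the exposure-adjusted incidence rate (EAIR) runs from first application to onset of the first event of that type.

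**The concern.** The definition recognises worsening and the assignment rule does not. An event that qualifies only because it worsened did not begin in any treatment period, so the rule gives it no table.

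An event that began before Week 12 and changed for the worse afterwards has a table, but possibly the wrong one for its later attributes. SAP 7.2 does not say that severity, seriousness, relationship or action taken in the primary tables stop at the first Period 3 application. For a crossover subject, a grade or causality reached on open-label TMB-001 could then be reported under Vehicle. That sits badly with the as-treated principle of the Safety population (SAP 2.3), and with Protocol 4.2, which counts on the crossover for additional safety data. For re-randomized subjects, worsening under BID or QD would be missing from the table meant to compare those regimens.

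**Working it through.** The plan gives no figure to reproduce, so the check applies the rule to event types. First dose is taken as Day 1 and Period 3 as starting on Day 85 (Visit 6 is scheduled for Day 84). The onset and worsening days are invented for illustration.

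| Event | Onset | Worsens | Table by start (SAP 7.2) | Period of worsening |
|---|---|---|---|---|
| Present at baseline | Day -10 | Day 30 | none | Periods 1-2 |
| Present at baseline | Day -10 | Day 110 | none | Period 3 |
| Began on vehicle, worsens after crossover | Day 50 | Day 110 | primary, Vehicle column | Period 3, on TMB-001 |
| Began in Period 2 | Day 50 | Day 60 | primary | Periods 1-2 |
| Began in Period 3 | Day 95 | Day 110 | open-label | Period 3 |

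The last two rows are placed correctly. The first three are not.

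**Rows 1 and 2.** These are TEAEs only by the worsening route. With a pre-dose onset they also break the addendum's EAIR: time at risk = onset date minus first application date, which is negative.

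**Row 3.** This event is a TEAE by onset, not by worsening, and it properly counts once in Vehicle incidence. What is misplaced is what happened to it on TMB-001. A TMB-001 subject re-randomized to BID or QD gives the same pattern: the event stays in the TMB-001 column and is missing from the BID/QD table. There the misplacement concerns period and dosing frequency, not drug against vehicle.

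**Scale.** SAP 1.3.2 plans up to 110 subjects at 2:1.

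- Vehicle arm: 110 / 3 = 36.7, about 37. One subject is 1 / 37 = 2.7 percentage points of an attribute row; two are 2 / 37 = 5.4 points.
- Crossover column: the number crossing over is not given. If it is 20, 30 or all 37, one missed subject is 1 / 20 = 5.0, 1 / 30 = 3.3 or 1 / 37 = 2.7 points.
- BID and QD columns: at most 74 subjects are re-randomized 1:1, so about 37 per arm at most, and one subject is at least about 2.7 points.

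These show what one subject is worth. They do not estimate how many would be affected.

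**The case against.** The best reply is that the protocol may already turn a worsening into a separate AE. Appendix 3 lists exacerbation of a pre-existing condition, in frequency or intensity and expressly including local skin reactions, as meeting the AE definition, and requires each event to be recorded separately. Table 1 (note f) and Section 8.3.1 send baseline examination abnormalities to medical history and record later worsening as an AE. Table 1 (note t) sends most health changes during screening to medical history. If the exacerbation record carries the date of worsening as its onset, the SAP rule places it correctly.

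This largely stands for pre-dose events, so the group that falls out of both tables is probably small. It does not settle the matter, because neither document says which onset date an exacerbation carries, and the SAP's separate worsening route would then have little to do. For AEs already on record, Appendix 3 says "New or updated information will be recorded in the originally completed eCRF". A reader might infer that a worsening therefore always keeps its original onset. The sentence does not say that: it sits among general follow-up duties and leaves the onset date open.

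A second reply is that other output captures the change. SAP 7.2.1 summarizes local skin reactions at every visit by grade, and as worsened or not from baseline. All AEs are listed. The TEAE proportions through Weeks 12 and 24 are introduced after the rule and are not expressly bound by it. Protocol 2.2 reports that Phase IIb skin reactions occurred mostly at Weeks 2 and 4, and Protocol 7.1 calls retinoid irritation transient, so late worsening of skin events need not be common. All of this limits the loss. None of it replaces the tables of seriousness, relationship and withdrawal.

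The Week 12 topline lock (SAP 3.1) does not supply the missing cut-off either: safety output there is optional, and the remaining analyses are run after the study ends.

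**Conclusion.** The rule as written gives a wrong placement in two situations: baseline events that worsen (no table, probably few), and AEs from Periods 1-2 whose severity, seriousness, relationship or action taken changes in Period 3. The second matters more. Such an event is missing from the open-label table, and its Period 3 attributes can enter the primary table under the initial arm, including Vehicle after crossover. Only attribute rows are affected. This rests on the change being entered as an update to the existing record and on no data cut being applied at the first Period 3 application; the documents exclude neither.

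A reader might go further and infer that the safety comparison is biased in favour of TMB-001. The documents do not support that. The TMB-001 column absorbs Period 3 attributes in the same way, from an arm twice as large, so the net direction is unknown. Nor is the Vehicle any-TEAE incidence inflated, since the subject is already counted there. The number of affected subjects cannot be derived; 2.7 points per vehicle subject is a scale only. No formal inference is planned on the Period 3 efficacy comparisons or on safety, so the stake is a correct description of harm by treatment received.

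**What to change.** In SAP 7.2, or by addendum:

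1. Assign a TEAE to the period in which it started or worsened. For Period 3, the reference is the subject's status at the first Period 3 application.
2. Assign events present at baseline to the period in which they worsened.
3. In the primary TMB-001/Vehicle tables, use severity, seriousness, relationship and action taken only up to the first Period 3 application.
4. Use the same treatment-emergent date for the EAIR time at risk in addendum 6.0.
5. State that a worsening of an ongoing AE is recorded with its own onset date.

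The same paragraph of SAP 7.2 points to Section 3.9.3 for the data presentations, which are in Section 3.11.3; correct this at the same time.

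The cost is SAP wording, programming and possibly one data query on AEs ongoing at Week 12.

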7.2.1 Local Skin Reactions

The incidences of local skin reactions (LSRs) will be summarized for all visits according to the skin irritation scale (Grade 0 – none, Grade 1 – mild, Grade 2 – moderate, Grade 3 – severe) and type of reaction (burning/stinging, erythema, erosions, and edema). Changes from baseline will also be summarized for all visits and will be categorized into

'worsened' and 'same or improved' categories. For subjects reporting more than one occurrence of the same type of reaction, the most severe reaction will be used for the summary.

The proportion of subjects experiencing a LSR through Week 12 will be reported along with exact binomial 95% confidence intervals, using the primary safety data presentation. The proportion of subjects experiencing a LSR through Week 24 will be reported along with exact binomial 95% confidence intervals, using the open-label dosing data presentation. Additionally, the Week 12 analysis will be repeated, separating subjects that had ≥ 10 Cetaphil applications within the first 21 days, versus subjects that had < 10 Cetaphil applications.

Additionally, the number and percentage of subjects who had suspected allergic contact dermatitis will be provided for all visits, along with exact binomial 95% confidence intervals. The number of subjects with confirmed cases of allergic contact dermatitis will be reported as well; subjects with confirmed cases are defined as those who had a suspected event reported, **and** allergic contact dermatitis reported as an AE.

A by-subject listing will be provided for all local skin reaction data.

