6.0 Adverse events – addition of exposure adjusted incidence rates

As requested by the FDA, all AE tables will include exposure adjusted incidence rates (EAIRs) per 100 years of exposure in addition to the number and proportion of subjects with AEs. Exposure adjusted incidence rates for a specific type of AE will be calculated as the number of subjects with the specific type of AE, divided by the total person-years at risk for the specific type of AE. For subjects with events, the time at risk is the time from the first IMP application to onset of the first event of the specific type, for subjects with no event of the specific type, the time at risk is the time from the first IMP application to the last visit.

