1.4.5 Safety Parameters

The safety endpoints include the following:

- Comparison of proportion of subjects experiencing local skin reactions (LSRs) through Week 12 between TMB-001 0.05% and vehicle-treated subjects.
- Comparison of proportion of subjects experiencing treatment-emergent adverse events (TEAEs) through Week 12 between TMB-001 0.05% and vehicle-treated subjects.
- Comparison of proportion of subjects experiencing LSRs through Week 24 between subjects randomized to TMB-001 0.05% BID and QD maintenance dosing.
- Comparison of proportion of subjects experiencing TEAEs through Week 24.
- Comparison of proportion of subjects demonstrating clinically confirmed allergic contact dermatitis by patch testing through Week 12 between TMB-001 0.05% and vehicle-treated subjects.

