3.11.3 Safety

The primary data presentation for all safety analyses (henceforth referred to as 'primary safety data presentation') will have the following table header:

TMB-001 0.05% (N=xx)	Vehicle (N=xx)	Overall (N=xx)
----------------------------	-------------------	-------------------

The TMB-001 0.05% and Vehicle columns will represent the subjects initially randomized to either TMB-001 0.05% or vehicle, regardless of the second randomization allocation in Period 3.

Additionally, a data presentation specific to Period 3 will be used:

	OL TMB-001 0.05% BID (N=xx)			
OL TMB-001 0.05% QD (N=xx)	TMB-001 0.05% in	Vehicle in Blinded	Total OL TMB- 001 0.05% BID (N=xx)	Overall (N=xx)

	Blinded Phase (N=xx)	Phase (N=xx)		
--	-------------------------	-----------------	--	--

This data presentation (henceforth referred to as 'open-label dosing safety data presentation') will be used for all analyses of safety endpoints specifically during Period 3, comparing TMB-001 0.05% BID and QD maintenance dosing.

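### Four safety endpoints are defined as between-arm comparisons, but the SAP plans no between-arm estimate or interval for any of them

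*SAP*

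**What the plan says.** SAP 1.4.5 words the Week 12 safety endpoints as contrasts between the randomised arms. For skin reactions it reads "Comparison of proportion of subjects experiencing local skin reactions (LSRs) through Week 12 between TMB-001 0.05% and vehicle-treated subjects". The TEAE endpoint takes the same form, with the same two arms and the same time point. For contact dermatitis the text is "Comparison of proportion of subjects demonstrating clinically confirmed allergic contact dermatitis by patch testing through Week 12 between TMB-001 0.05% and vehicle-treated subjects". The Week 24 skin-reaction endpoint sets BID against QD maintenance. These match endpoints 8a, 8b, 9 and 8c in the protocol synopsis and Table 2.

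The analysis text is different in kind. SAP 7.2.1 states "The proportion of subjects experiencing a LSR through Week 12 will be reported along with exact binomial 95% confidence intervals", and SAP 7.2 states that "the proportion of subjects experiencing a TEAE through Week 12 will be reported along with exact binomial 95% confidence intervals". Both sections repeat this for Week 24 in the open-label presentation. For endpoint 9, the exact interval in SAP 7.2.1 is attached to suspected cases; for confirmed cases the text is "The number of subjects with confirmed cases of allergic contact dermatitis will be reported as well".

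SAP 3.11.3 sets the columns of the main safety tables as TMB-001, Vehicle and Overall: "The TMB-001 0.05% and Vehicle columns will represent the subjects initially randomized to either TMB-001 0.05% or vehicle". There is no column for a contrast. Section 6.0 of the addendum says "all AE tables will include exposure adjusted incidence rates (EAIRs) per 100 years of exposure", with neither an interval nor a contrast.

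**The concern.** A proportion with its own interval describes one arm. It does not estimate the quantity that the endpoint names, and it does not show how large an excess of reactions remains compatible with the data. Protocol 2.3 and 7.1 expect skin irritation with a retinoid, and Protocol 7.1 notes that the vehicle may also cause it. The excess over vehicle is therefore the natural tolerability question, and the tables as planned leave it unestimated.

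The gap is not declared. SAP 8.0 lists the changes from the protocol analyses and does not mention the safety comparisons. It is also not the SAP's general practice: SAP 5.3.2 and 5.4 disclaim formal inference for other secondary and patient-reported endpoints, yet still plan a difference in proportions with a 95% interval.

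**Working it through.** **Endpoint against planned output**

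| Endpoint | Contrast named in SAP 1.4.5 | Output in SAP 7.2 / 7.2.1 |
|---|---|---|
| 8a LSR, Week 12 | TMB-001 vs vehicle | proportion and exact 95% CI per column |
| 8b TEAE, Week 12 | TMB-001 vs vehicle | proportion and exact 95% CI per column |
| 8c LSR, Week 24 | BID vs QD | proportion and exact 95% CI per column |
| 9 confirmed allergic contact dermatitis, Week 12 | TMB-001 vs vehicle | count |

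**The plan's own figure.** The documents give no power or precision figure for safety. The only one is for the primary efficacy endpoint (SAP 1.3.3): 110 subjects, 2:1, 50% vs 10%, two-sided alpha 0.01, about 90% power, about 15% dropout. It reproduces. The continuity-corrected two-proportion formula gives 32 vehicle and 96 in total, and 96/0.85 = 113, close to 110. Power at 62 vs 31 (110 less 15%) is 0.891. The trial was thus sized for a 40-point efficacy difference.

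**Inputs for the safety check**
- Arm sizes: 110 × 2/3 ≈ 73 and 110 × 1/3 ≈ 37.
- BID vs QD: SAP 1.3.2 allows up to 74 re-randomised subjects, so at most 37 per arm; 25 per arm is an assumed lower value.
- True event rates: assumed. Protocol 2.2 reports 18% for burning/stinging and erythema by Week 12 on 0.05% in Phase IIb (n = 11), and no vehicle rate.

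**Method.** Both binomials were enumerated in full. For each pair of counts (x1, x2), two things were recorded: whether the two Clopper-Pearson 95% intervals fail to overlap, and whether the Newcombe 95% interval for p1 − p2 excludes zero. Each probability is the sum of Bin(x1; n1, p1) × Bin(x2; n2, p2) over the qualifying pairs.

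| n | True rates | Arm intervals separate | Difference CI excludes 0 |
|---|---|---|---|
| 73 vs 37 | 40% vs 20% | 21.1% | 57.5% |
| 73 vs 37 | 50% vs 30% | 17.8% | 52.8% |
| 73 vs 37 | 50% vs 20% | 58.6% | 89.2% |
| 73 vs 37 | equal, 20% or 30% | 0.31–0.33% | 4.8–5.0% |
| 62 vs 31 | 40% vs 20% | 15.5% | 49.8% |
| 37 vs 37 (BID vs QD, maximum) | 40% vs 20% | 12.2% | 47.5% |
| 25 vs 25 (BID vs QD, assumed) | 40% vs 20% | 6.6% | 35.2% |

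When the arms are equal, the intervals separate in about 0.3% of trials instead of 5%. Separation is therefore far stricter than a 95% comparison.

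**One worked data set: 29/73 and 7/37**
- Exact intervals: 39.7% (28.5 to 51.9) and 18.9% (8.0 to 35.2). They overlap.
- Difference: 0.3973 − 0.1892 = 0.2081.
- Wilson limits: (0.2929, 0.5119) and (0.0948, 0.3420).
- Newcombe lower limit: 0.2081 − √[(0.3973 − 0.2929)² + (0.3420 − 0.1892)²] = 0.2081 − 0.1851 = 0.023.
- Newcombe upper limit: 0.2081 + √[(0.5119 − 0.3973)² + (0.1892 − 0.0948)²] = 0.2081 + 0.1485 = 0.357.

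The difference is 20.8 points, 95% CI 2.3 to 35.7. The planned tables would show the two overlapping intervals and not this one.

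**The case against.** Safety is meant to be descriptive. SAP 3.2.2 confines formal testing to primary and key secondary efficacy, and Protocol 10.3.1.2 summarises safety by treatment group. The word comparison is also used loosely: endpoint 8d carries it with no comparator named. This explains the absence of a test. It does not explain the absence of an estimate, since the SAP gives differences with intervals for other endpoints that it does not test.

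Counts and denominators will be in the tables, so a reader can compute a crude difference, as was done above. Readers will also see events by severity and relationship, reactions by visit and grade, and exposure-adjusted rates. This stands: no information is lost. What is missing is a prespecified estimate of a prespecified endpoint.

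Part of the weak separation is due to sample size. At 40% vs 20% the difference interval itself still includes zero in 42.5% of trials (100 − 57.5). This also stands. The difference interval does, however, show the excess still compatible with the data.

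A reader might go further and infer that the plan will judge safety as similar because arm intervals overlap, or that it would miss most relevant harms. The documents support neither. They contain no claim of similar safety, no overlap rule, no margin and no relevant harm size. Overlap is also not the usual result at large excesses: the arm intervals separate in 59% of trials at 50% vs 20% and in 89% at 60% vs 20%.

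**Conclusion.** The point holds as a gap between endpoint and analysis: 8a, 8b, 8c and 9 are comparisons, and no between-arm estimate or interval is planned for any of them. Endpoint 9 is the weakest, with a count alone. This part rests on the text and needs no assumption.

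The size of the practical disadvantage does rest on assumptions. At true rates of 40% vs 20%, arm intervals separate in 21% of trials at 73 vs 37, against 58% in which a difference interval excludes zero. For BID vs QD the figures are 7% vs 35% at 25 per arm and 12% vs 47% at 37 per arm. These rates are illustrative, and the contrast between the two methods narrows as the true excess grows. The change should be made because it is cheap and lets the trial report the comparison that it names. It does not imply that the planned tables are misleading in themselves.

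**What to change.** In SAP 7.2 and 7.2.1, add the unstratified risk difference with a two-sided 95% interval, by the Newcombe or the Miettinen-Nurminen method (name one in advance), as description without a hypothesis test:

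- for 8a, 8b and 9: TMB-001 against vehicle, through Week 12;
- for 8c: BID against QD, restricted to subjects initially on TMB-001 who were re-randomised at Week 12. Vehicle crossovers were assigned to BID without randomisation, so the contrast should not use the total BID column of the open-label presentation.

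An unstratified estimate avoids a later choice of strata when counts are small, and fits the Period 3 randomisation, which has no stratification factors (SAP 1.3.2). Keep the per-arm exact intervals. Add one sentence saying that neither overlapping arm intervals nor a difference interval that includes zero shows similar safety.

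Cost: a sentence or two in each section and one extra table column. No new data are needed, and nothing changes in the efficacy testing.
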